2.1.1.4 Baseline

Baseline for safety is the last assessment (including unscheduled visits) obtained on or before the day of the first dose of study treatment. All assessments obtained after the first dose of study treatment are considered as post-baseline unless otherwise specified.

Baseline for efficacy is comprised of the 7 days prior to Day 1 (Randomization Day) for UAS7 and other assessment on or prior randomization day.

2.1.1.5 On-treatment

All safety events happened after first dose of study treatment will be considered on-treatment no matter if during treatment period or follow-up period.

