Subjects may take an additional second generation H1-antihistamine that is eliminated primarily via renal excretion (eg cetirizine, levocetirizine or bilastine) as rescue medication (see [Section 6.2.3](#)). The rescue H1-antihistamine must differ from the background H1-antihistamine

and may only be administered to treat unbearable symptoms (itch) of CSU on a day-to-day basis throughout the study (from Day -14 until Day 113).

All other CSU therapies (including H1-antihistamines at higher than approved doses) are prohibited (see [Table 6-3](#) in [Section 6.6.2](#)).

An outline of the study design including three periods is presented in [Figure 3-1](#), while a detailed visit and assessment schedule can be found in [Table 8-1](#):

- Screening period (10-14 days prior to randomization): During the screening period, subjects who have provided informed consent will be assessed for study eligibility.
- Treatment period (Day 1 to Day 85): After screening, eligible subjects will be randomly assigned to one of the following treatment arms in a 1:1:1:1:1:1:1 ratio:
 - 10 mg LOU064 once daily
 - 35 mg LOU064 once daily
 - 100 mg LOU064 once daily
 - 10 mg LOU064 twice a day
 - 25 mg LOU064 twice a day
 - 100 mg LOU064 twice a day
 - Placebo
- Follow-up period (Day 86 to Day 113): subjects are followed-up [REDACTED] to further assess safety.

[figure not shown]
An extension study is in development. Eligible subjects may roll-over into the extension study at Week 12 or at Week 16 (after completing all scheduled assessments planned at these visits), following roll-over criteria defined in the extension study protocol. The details of the study design and procedures of the extension, if implemented, will be described in a separate protocol.

[REDACTED]

[REDACTED]

[REDACTED]

Figure 3-1 Study Design

¹⁾ Background therapy is **1** generation H1-antihistamine at a locally approved licensed posology that must be administered every day with a stable treatment regimen throughout the study (from Day -14 until Day 113).

²⁾ Rescue therapy is a second generation H1-antihistamine at a locally approved licensed posology that is eliminated primarily via renal excretion (eg cetirizine, levocetirizine or bilastine). The rescue H1-antihistamine must differ from the background H1-antihistamine and may only be given to treat unbearable symptoms (itch) of CSU on a day-to-day basis throughout the study (from Day -14 until Day 113).

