12.5.2 Safety endpoints

All safety endpoints (i.e. AEs, laboratory data, vital signs, and ECG as well as potential risks defined in the safety profiling plan) will be summarized by treatment for all subjects of the safety set. All data will be included in the analysis regardless of rescue medication use.

Adverse events

All information obtained on adverse events will be displayed by treatment group and subject.

The number (and percentage) of subjects with treatment emergent AEs (events started after the first dose of study treatment or events present prior to the first dose of study treatment but increased in severity based on preferred term) will be summarized in the following ways:

- by treatment, primary system organ class and preferred term
- by treatment, primary system organ class, preferred term and maximum severity
- by treatment, Standardized MedDRA Query (SMQ) and preferred term

All AEs with onset in the follow-up period will be considered as treatment emergent. A subject with multiple AEs within a primary system organ class is only counted once towards the total of the primary system organ class.

Summaries will also be presented for AEs by severity and for study treatment related AEs.

If a subject reported more than one AE with the same preferred term, the AE with the greatest severity will be presented. If a subject reported more than one AE within the same primary system organ class, the subject will be counted only once with the greatest severity at the system organ class level, where applicable. All AEs with onset in the follow-up period will also be summarized separately.

Separate summaries will be provided for study medication related AEs, deaths, SAEs, and other significant AEs leading to discontinuation.

All AEs including the non-treatment emergent AEs will be listed.

Laboratory data

The summary of laboratory evaluations will be presented for two groups of laboratory tests (hematology and serum chemistry). Descriptive summary statistics for the change from baseline to each study visit will be presented. These descriptive summaries will be presented by test group, laboratory test and treatment group. Change from baseline will only be summarized for subjects with both baseline and post baseline values.

All laboratory data will be listed by treatment group, subject, and visit/time and if normal ranges are available abnormalities will be flagged.

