EOS	End of study period
E ₀	Expected Placebo Effect
FAS	Full Analysis Set
GCP	Good Clinical Practice
HSS7	Weekly Hives Severity Score
Ig	Immunoglobulin
INR	International Normalized Ratio
IRT	Interactive Response Technology
ISS7	Weekly Itch Severity Score
LLN	Lower Limit of Normal
LLOQ	Lower Limit of Quantification
MAR	Missing at Random
MedDRA	Medical Dictionary for Drug Regulatory Affairs
PD	Pharmacodynamics
PK	Pharmacokinetics

q.d.	Qua'que di'e / once a day
QTcF	QT interval corrected by Fridericia's formula
SAE	Serious Adverse Event
SAP	Statistical Analysis Plan
SD	Standard Deviation
SMQ	Standardized MedDRA Query
SOC	System Organ Class
TBL	Total bilirubin
T _{max}	The time to reach the maximum concentration after drug administration [time]
ULN	Upper Limit of Normal
ULOQ	Upper Limit Of Quantification
UPDD	Urticaria Patient Daily Diary

1 Introduction

Data will be analyzed by Novartis according to the data analysis section 12 of the study protocol which is available in [Appendix 16.1.1 of the CSR](#). Important information is given in the following sections and details are provided, as applicable, in [Appendix 16.1.9 of the CSR](#).

This document covers statistical and analytical plans for the

analysis of all data collected up to end of the study for CLOU064A2201 study with reference to the study protocol.

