2.7.1 Adverse events (AEs)

All information obtained on adverse events will be displayed by treatment group and any LOU064 dose.

Treatment-emergent events are defined as any events started on or after the first dose of study treatment day or any events presented prior to the first dose of study treatment day but increased in severity based on preferred term and before end of the study.

The number (and percentage) of subjects with treatment- emergent AEs will be summarized in the following ways:

- by primary system organ class and preferred term
- by primary system organ class, preferred term and maximum severity
- by Standardized MedDRA Query (SMQ) and preferred term

Summaries will also be presented for AEs by severity and for study treatment related AEs.

Separate summaries will be provided for deaths, SAEs, and other significant AEs such as AEs leading to discontinuation and AEs leading to treatment interruption.

If a subject reported more than one AE with the same preferred term, the AE with the greatest severity will be presented. If a subject reported more than one AE within the same primary system organ class, the subject will be counted only once with the greatest severity at the system organ class level, where applicable.

All AEs and SAEs including the non-treatment emergent AEs will be listed.

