2.7.1.1 Adverse events of special interest / grouping of AEs

Crude incidence rate for adverse events of special interest will be provided. The latest project eCRS will be used for reporting.

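### AEs of special interest are reported only as crude incidence although time at risk can be 12 or 16 weeks; exposure-adjusted rates and a listed follow-up AE table would be a cheap improvement

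*SAP*

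**What the plan says.** SAP 2.1.1.5 defines the on-treatment window: "All safety events happened after first dose of study treatment will be considered on-treatment no matter if during treatment period or follow-up period". SAP 2.7.1 is consistent with this: "Treatment-emergent events are defined as any events started on or after the first dose of study treatment day", with no cut at the last dose. The summary measure there is a count and percentage: "The number (and percentage) of subjects with treatment- emergent AEs will be summarized in the following ways". For AESIs, SAP 2.7.1.1 says: "Crude incidence rate for adverse events of special interest will be provided". No subject-time denominator for AEs appears in the public text.

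Protocol Section 3 places treatment at Day 1 to Day 85 and follow-up at Day 86 to Day 113, and allows two exit times: "Eligible subjects may roll-over into the extension study at Week 12 or at Week 16". Protocol 9.2 repeats this. The extension was still in development, and its entry criteria are in a separate protocol.

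Protocol 12.5.2 sets the rule for follow-up events, "All AEs with onset in the follow-up period will be considered as treatment emergent", and adds a second display: "All AEs with onset in the follow-up period will also be summarized separately". SAP 2.7.1 does not list that display. However, the SAP introduction says "Data will be analyzed by Novartis according to the data analysis section 12 of the study protocol", and SAP Section 4 declares no change to the protocol's analyses.

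**The concern.** A subject who enters the extension at Week 12 contributes 12 weeks in which an event can be counted. One who completes follow-up contributes 16. A percentage of subjects treats the two alike. If one arm sends more subjects into the extension at Week 12, or loses more early, its crude incidence falls for that reason alone.

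The trial is meant to choose a regimen on benefit and risk across six doses (protocol 4.1), so AESI rates will be compared between arms. A rate that allows for time at risk is the more suitable measure.

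The second issue is readability. The last 4 weeks are drug-free. If an AE risk exists on drug and fades off drug, the pooled figure shows a weaker contrast with placebo than the treatment period does. The protocol's follow-up summary lets a reader separate the two, but the SAP's own list of AE tables does not carry it.

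**Working it through.** **Inputs from the documents.** Treatment lasts 12 weeks and follow-up 4 weeks (protocol summary). Follow-up runs from Day 86 to Day 113 (protocol Section 3). There are 44 subjects per arm (protocol Section 5).

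**Plan's own figures.** 2 + 12 + 4 = 18 weeks, as stated. Follow-up is 113 − 86 + 1 = 28 days, or 28/113 = 24.8% of the post-randomization time of a subject who completes it, against 0% for a Week 12 roll-over. The ratio of maximum time at risk is 16/12 = 1.33.

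**Assumptions.** The documents give neither AE rates nor roll-over shares. I assume a constant hazard, equal in both arms and on and off drug, 12-week risks r12 of 20%, 30% and 50%, and Week 12 roll-over shares s that differ between arms.

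**Formulas.**
- Weekly hazard: h = −ln(1 − r12)/12
- 16-week risk: r16 = 1 − exp(−16h)
- Crude risk in an arm: s × r12 + (1 − s) × r16
- False difference between two arms: (difference in s) × (r16 − r12)
- Standard error of a difference, 44 per arm: √(2 × r12 × (1 − r12)/44)

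**Results** (differences, gaps and standard errors in percentage points).

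| r12 | r16 | gap | 80% vs 60% | 80% vs 40% | 90% vs 30% | standard error |
|---|---|---|---|---|---|---|
| 20% | 25.7% | 5.7 | 1.1 | 2.3 | 3.4 | 8.5 |
| 30% | 37.8% | 7.8 | 1.6 | 3.1 | 4.7 | 9.8 |
| 50% | 60.3% | 10.3 | 2.1 | 4.1 | 6.2 | 10.7 |

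Worked row, r12 = 30%: h = 0.3567/12 = 0.02972 and r16 = 1 − exp(−0.4756) = 37.85%. With 80% roll-over, the crude risk is 0.8 × 30 + 0.2 × 37.85 = 31.57%. With 40%, it is 0.4 × 30 + 0.6 × 37.85 = 34.71%. The difference is 3.14 points although the risk is the same. With equal roll-over in both arms it is zero.

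**What the proposed rate would show.** In the worked row, subjects with an event divided by subject-time to first event or exit estimates h in both arms, 2.97 per 100 subject-weeks, whatever the roll-over shares. The false difference disappears.

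**Pooled comparison.** The SAP also presents all LOU064 doses together, 6 × 44 = 264 subjects. The standard error against placebo is √(r12 × (1 − r12) × (1/264 + 1/44)) = 6.5, 7.5 and 8.1 points, still above the shifts in the table.

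**Drug-free weeks.** If an on-drug rate ratio of 2 falls to 1 off drug (assumption), the ratio over 16 weeks is (12 × 2 + 4 × 1)/16 = 1.75. Exposure adjustment over the whole study does not undo this. Only a display that separates the periods shows it.

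**The case against.** The strongest reply is that the pooling is the protocol's own rule. Protocol 12.5.2 counts follow-up events as treatment emergent. Protocol 10.1.1 asks for AE monitoring for at least 30 days after the last dose, and the 28 follow-up days lie inside that window. This stands: a reader might infer that labelling these events as on-treatment is a mistake, but the documents do not support that.

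A reader might also infer that the SAP has dropped the separate follow-up summary. That is not shown either. The SAP defers to protocol Section 12 and declares no change, so the table remains planned. It is only missing from the list in SAP 2.7.1.

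A third tempting reading is that roll-over depends on disease activity, and so on dose, and therefore biases the AE comparison. Neither document says so. The criteria are in the extension protocol, and the extension was conditional on being implemented.

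Finally, an imbalance would be visible. SAP 2.4.1 summarizes duration of exposure and of study by arm, and SAP 2.3.1 tabulates Week 12 and Week 16 completion. Safety is descriptive, with no AE test in the visible text. This lowers the stakes, but a reader who sees unequal follow-up would still have no adjusted rate to turn to.

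The case for replacing the main tables with ones cut at the Week 12 visit is weak. Such tables would depart from protocol 12.5.2 and could miss reactions to the last dose, since the Week 12 morning dose is taken at that visit (protocol 6.1.3). They would also still include off-drug time of subjects who stop treatment early and stay in the study.

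**Conclusion.** This is a cheap improvement, not an error in the plan. Crude AESI incidence is the less suitable measure when the design itself allows 12 or 16 weeks at risk, and a better one can be computed from dates the SAP already uses for duration of study.

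The possible distortion is modest: 2.3 to 4.1 points under an assumed 80% versus 40% roll-over, and up to 6.2 points at 90% versus 30%. Each is below the standard error at 44 per arm, smaller imbalances give proportionally less, and equal roll-over gives none. All of this rests on assumed risks, assumed roll-over shares and a constant hazard. The documents show that unequal time at risk is possible. They do not show that it differs by arm.

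One limit remains. The SAP's document history mentions a revised censoring rule for a time-to-event analysis, in a section that is withheld. Whether it covers AEs cannot be known, so the absence of a time-adjusted AE analysis can be stated only for the public text.

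**What to change.** Keep the protocol's treatment-emergent definition and the main AE tables as they are. Then:

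1. In SAP 2.7.1.1, show exposure-adjusted incidence beside the crude incidence for AESIs: subjects with at least one event divided by total subject-time from first dose to first event, with subjects without an event censored at roll-over or last visit.
2. In SAP 2.7.1, list the separate summary of AEs with onset in follow-up that protocol 12.5.2 already promises, so that treatment-period and drug-free events can be read apart.

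The cost is a few lines of SAP text and a few extra standard tables. No new data are needed.

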2.2 Analysis sets

The following analysis sets will be used for the data analysis, details refer to [section 5.5](#).

The **Randomized Set** will consist of all randomized subjects, regardless of whether or not they actually received study medication. Subjects will be analyzed according to the treatment assigned to at randomization.

The **Full Analysis Set (FAS)** will consist of all randomized subjects. Following the intent-to-treat principle, subjects will be analyzed according to the treatment and strata assigned to at randomization. Mis-randomized subjects (mis-randomized in IRT) will be excluded.

Mis-randomized subjects are defined as cases where IRT contacts were made by the site either prematurely or inappropriately prior to confirmation of the subject's final randomization eligibility and no study medication was administered to the subject.

The **Safety Set** will consist of all subjects who received at least one dose of study medication whether or not being randomized. Subjects will be analyzed according to treatment received.

If a subject has received the wrong treatment during more than 50% of the time of the entire treatment period, the treatment received will be set to this wrong treatment; otherwise it will be set to the original assigned treatment. Except for patients assigned to placebo arm, they will be summarized under LOU064 in case they took LOU064 during the treatment period independent of the time on LOU064.

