6.1 Study treatment

There will be 3 dispensing visits: Randomization, Week 4 and Week 8.

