12.1 Analysis sets

The Randomized Set will consist of all randomized subjects, regardless of whether or not they actually received study medication. Subjects will be analyzed according to the treatment

assigned to at randomization. Unless otherwise specified, mis-randomized subjects (mis-randomized in IRT) will be excluded from the randomized set. Mis-randomized subjects are defined as cases where IRT contacts were made by the site either prematurely or inappropriately prior to confirmation of the subject's final randomization eligibility and no study medication was administered to the subject.

The Full Analysis Set (FAS) will consist of all randomized subjects who received at least one dose of study medication. Following the intent-to-treat principle, subjects will be analyzed according to the treatment and strata assigned to at randomization. Mis-randomized subjects (mis-randomized in IRT) will be excluded.

The Safety Set will consist of all subjects who received at least one dose of study medication whether or not being randomized. Subjects will be analyzed according to treatment received.

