2.7 Safety analyses

All safety endpoints (i.e. AEs, laboratory data, vital signs, and ECG as well as potential risks defined in the safety profiling plan) will be summarized by actual treatment group using the safety set.

All data will be included in the analysis regardless of rescue medication use.

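### The treatment-received rule in SAP 2.2 keeps LOU064-exposed subjects out of the placebo safety column only if they were assigned to placebo

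*SAP*

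**What the plan says.** Protocol 12.1 gives only the principle for the Safety Set: "Subjects will be analyzed according to treatment received". It does not deal with mixed exposure. SAP 2.2 adds the operating rule in two steps.

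- General rule: "If a subject has received the wrong treatment during more than 50% of the time of the entire treatment period", then "the treatment received will be set to this wrong treatment; otherwise it will be set to the original assigned treatment". Placebo is not excluded as a destination.
- Exception: "Except for patients assigned to placebo arm", of whom the SAP says "they will be summarized under LOU064 in case they took LOU064 during the treatment period independent of the time on LOU064".

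Two other SAP provisions decide what follows. Section 2.7 says that safety endpoints "will be summarized by actual treatment group using the safety set". Section 2.1.1.5 says: "All safety events happened after first dose of study treatment will be considered on-treatment no matter if during treatment period or follow-up period". SAP 2.1.1.1 lists the groups to be presented: six LOU064 regimens, a pooled Any LOU064 group, and placebo. Section 2.2 does not say which of the LOU064 groups receives a placebo-assigned subject who took LOU064.

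**The concern.** The exception adopts a sensible principle: a subject exposed to LOU064 should not be part of the placebo safety reference, however short the exposure. The SAP applies it according to the assigned arm, although the reason for it is the exposure. A placebo-assigned subject leaves placebo after a single LOU064 dose. A LOU064-assigned subject with weeks on drug enters placebo once placebo time passes one half.

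The placebo column is the reference for judging six regimens in a dose-selection study. Protocol 4.6 names infection, bleeding, cytopenia and cardiovascular effects as potential risks needing close monitoring. For uncommon events of this kind, one or two misplaced subjects can alter how a column of about 44 reads.

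A smaller gap sits beside this one. A placebo-assigned subject who took LOU064 has no stated dose column. If that subject is counted only in Any LOU064, the six dose columns no longer sum to the pooled column. The vital-signs summaries (SAP 2.7.4.2) and the normal-range laboratory shift tables (SAP 2.7.3) mention only treatment group, so the subject's place there is unclear.

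**Working it through.** The plan states no figure on this point, so there is none to reproduce. The check applies the rule literally to subjects with mixed exposure.

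**Inputs**
- Treatment period T: Day 1 to Day 85, 12 weeks (Protocol 3 and 6.1.3), taken as 84 or 85 days.
- Threshold: wrong treatment for more than 50% of T (SAP 2.2).
- Dispensing: "There will be 3 dispensing visits: Randomization, Week 4 and Week 8" (Protocol 6.1), hence three blocks of about 28 days.
- Arm size: about 44 (Protocol 5).

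**Most LOU064 time that can sit under placebo.** Find the smallest number of placebo days d with d/T > 0.5; the remainder, T − d, is time on LOU064.
- T = 84: 42/84 is exactly 50% and does not qualify. d = 43 (51.2%) does, leaving 41 LOU064 days (41/84 = 48.8%).
- T = 85: 42/85 = 49.4% does not qualify. d = 43 (50.6%) does, leaving 42 LOU064 days (42/85 = 49.4%).

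**Errors over whole dispensing blocks (LOU064-assigned subject given placebo, T = 84)**

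| Wrong blocks | Placebo share | Set to | LOU064 days |
|---|---|---|---|
| 1 of 3 | 28/84 = 33.3% | Assigned LOU064 arm | 56 |
| 2 of 3 | 56/84 = 66.7% | Placebo | 28 |
| 3 of 3 | 84/84 = 100% | Placebo | 0 |

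Only the middle row is a problem. In the last row the subject took no LOU064, and placebo is the right column.

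**Do the events follow the subject?** Yes. Section 2.7 tabulates by actual treatment group, and section 2.1.1.5 counts every event after first dose without limiting it to time on the labelled treatment. An event during the 28 LOU064 days is therefore a placebo event in the tables.

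**Effect on a placebo percentage.** Assume k such subjects, each with the event, and no other placebo case among 44. Each subject adds to both numerator and denominator, so the result is k/(44 + k).
- k = 1: 1/45 = 2.2%
- k = 2: 2/46 = 4.3%
- k = 3: 3/47 = 6.4%

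These values of k are illustrations; the documents give no expected number.

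**After the fix.** With the any-LOU064 principle applied to every arm, LOU064 days counted under placebo fall from a maximum of 41 or 42 per reclassified subject to zero.

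**The case against.** The strongest reply is that the case will hardly ever arise. A LOU064-assigned subject must be on placebo for more than half of the period. SAP 1.1 runs that period to the scheduled Week 12 visit even for those who stop early, so an early stopper could rarely reach the threshold. Kits are assigned by medication number through the IRT and their labels are kept in the source document (Protocol 6.3.2 and 6.7). Of the six arms that a LOU064 subject could wrongly receive, five are other LOU064 regimens. The event must then fall in the remaining LOU064 weeks. An affected subject would also be visible: treatment errors go on the eCRF (Protocol 10.1.5), deviations are tabulated (SAP 2.3.1), and daily intake and all adverse events are listed (SAP 2.4.1 and 2.7.1). This all stands, and it limits the point to a minor one. It does not make the placement correct.

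A majority-exposure rule is a defensible choice in itself, and keeping a mostly-placebo subject in a LOU064 column dilutes that column. That is a real but slight cost. The SAP has already set majority exposure aside for placebo-assigned subjects, and the same reasoning applies to the others.

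The exception can also be parsed differently, so that the any-LOU064 rule covers everyone except the placebo arm. That reading is strained. It would remove the problem above but leave placebo-assigned subjects with up to half their time on LOU064 in the placebo column. Either reading calls for a rewrite.

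Three stronger inferences are tempting and should be resisted.
- A reader might conclude that the rule cannot be programmed. It can: Any LOU064 is a listed group. What is missing is whether a dose column is used too.
- A reader might say that the placebo safety data are contaminated. The documents show only that the rule would permit this in a rare case.
- A reader might object that a placebo-assigned subject's events from before the first LOU064 dose move to LOU064. Any subject-level as-treated assignment does this, so it is no particular fault of this rule.

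**Conclusion.** The point holds as a minor correction. On its natural reading, SAP 2.2 gives a wrong placement for one type of subject, and nothing elsewhere in the protocol or SAP puts it right. This is a consequence of a stated rule and goes beyond missing detail.

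The size per affected subject is up to 41 or 42 LOU064 days under placebo, or 28 days in the two-of-three-dispensings case. One affected subject with an event changes placebo from 0/44 to 1/45 (2.2%). That percentage assumes the subject has the event and that placebo otherwise has none of that type. How often it would happen is unknown, since no misdosing rate is given; it should be rare. Efficacy is unaffected, because the Full Analysis Set follows the assigned treatment.

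**What to change.** Replace the exception in SAP 2.2 with statements to this effect:

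1. A subject who took at least one dose of LOU064 is never summarized under placebo, whatever the assigned arm. A LOU064-assigned subject who took some LOU064 and whose wrong treatment was placebo stays in the assigned LOU064 column.
2. A placebo-assigned subject who took LOU064 is summarized under the LOU064 regimen actually received and in Any LOU064, so that the dose columns sum to the pooled column. If there was more than one regimen, use the one taken longest.
3. Any tie rule names its scale. A rule based simply on the higher dose is undefined here: 10 mg q.d. and 10 mg b.i.d. are equal per intake, and 35 mg q.d. against 25 mg b.i.d. reverses between per-intake dose and daily total (35 against 2 × 25 = 50 mg). Total daily dose would serve, since the six regimens give 10, 20, 35, 50, 100 and 200 mg, all distinct.

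Flagging events before the first LOU064 dose in the listings is optional.

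The cost is a few sentences and a small change to the treatment-received derivation, with no new data. SAP amendment 3.0 was issued before final database lock and already edited the analysis-set exclusion rules, so a change of this kind fitted that stage. The price is slight dilution of a LOU064 column by a mostly-placebo subject.
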